#### **Model Results Presentation**

#### Overall Estimate of % Change in BMD:

- The overall raw percentage change in BMD per year along with the LS means ratio and % change from baseline will be presented by treatment.
- In addition, the LS means ratio and % change from baseline for the treatment comparison will also be produced.

#### Estimates of % Change in BMD by visit:

- For each visit the raw baseline, raw mean and raw % change from baseline will be presented by treatment.
- The adjusted mean and adjusted ratio to baseline will be produced along with the % change from baseline by treatment.
- In addition, the LS means treatment difference for the ratio and % change at visit along with the % change per annum will be produced.

All LS means will be presented with their associated 95% confidence intervals.

#### Plots of BMD:

 Plots of raw mean, raw % change from baseline and LS mean percentage change from baseline by visit will be generated for each treatment.

## 7.2. Secondary Safety Analyses

## 7.2.1. Endpoint / Variables

- Bone mineral density measured at the Total Hip by Gender
- Bone mineral density measured at the Lumbar Spine L1-L4
- Bone mineral density measured at the Lumbar Spine L1-L4 by Gender

## 7.2.2. Summary Measure

• Percentage change from baseline

### 7.2.3. Population of Interest

The secondary analyses will be based on the Safety populations, unless otherwise specified.

#### 7.2.4. Strategy for Intercurrent (Post-Randomisation) Events

See Section 7.1.4.

### 7.2.5. Statistical Analyses / Methods

Details of the planned displays are provided in Appendix 12: List of Data Displays and will be based on GSK data standards and statistical principles.

Unless otherwise specified, endpoints / variables defined in Section 7.2.1 will be summarised using descriptive statistics, graphically presented (where appropriate) and listed.

#### 7.2.5.1. Statistical Methodology Specification

#### Endpoint(s)

- Bone mineral density measurements by Gender
- Bone mineral density measured at the Lumbar Spine (L1-L4)
- Bone mineral density measured at the Lumbar Spine (L1-L4) by Gender

#### **Model Specification**

- See Section 7.1.5.1.
- For the models of bone mineral density measurements by Gender, each gender will have their own model fitted excluding any data from the opposite gender (split model).

## **Model Checking & Diagnostics**

See Section 7.1.5.1.

#### Model Results Presentation

• See Section 7.1.5.1.

## 7.3. Adverse Events Analyses

Adverse events analyses including the analysis of adverse events (AEs), Serious (SAEs) and other significant AEs will be based on GSK Core Data Standards. The details of the planned displays are provided in Appendix 12: List of Data Displays.

## 7.4. Adverse Events of Special Interest Analyses

A comprehensive list of MedDRA terms based on clinical review will be used to identify each type of event. Changes to the MedDRA dictionary may occur between the start of the study and the time of reporting and/or emerging data from on-going studies may highlight additional adverse events of special interest, therefore the list of terms to be used for each event of interest and the specific events of interest will be based on the safety review team (SRT) agreements in place at the time of reporting. These will be produced for both LABA and ICS AESIs. The details of the planned displays are provided in Appendix 12: List of Data Displays.

#### 7.5. On-treatment Fractures

Fracture events including the number and percentage of subjects recorded as having at least one bone fracture, location of fractures and whether they were traumatic or not traumatic (severity) will be summarised. If a subject suffers fractures in multiple locations with the same date of fracture, this is considered to be one fracture incident. The frequency and percentage of subjects with 0, 1, 2 and more than 2 fracture incidents will also be summarised.

In addition, the rates of fractures will be summarised as described in Section 9.6.3. The details of the planned displays are in Appendix 12: List of Data Displays.

#### 7.6. On-treatment Pneumonia

Pneumonia events including severity, outcomes, those supported by x-rays, those within 14 days of moderate/severe exacerbations and number of events per subject will be summarised.

A chest x-ray/CT scan is associated with pneumonia if it is performed within the duration of the pneumonia or between -7 to +10 days (inclusive) of the date of onset.

In addition, the rates of events will be summarised as described in Section 9.6.3. The details of the planned displays are in Appendix 12: List of Data Displays.

## 7.7. On-treatment Moderate/Severe COPD Exacerbations

The number and percentage of subjects reporting an on-treatment moderate/severe exacerbation along with the outcome category (fatal, resolved or not resolved), result (withdrawal, treatment by corticosteroids, antibiotics, emergency room visits or hospitalisations) will be presented along with the primary cause.

A moderate COPD exacerbation is defined as requires treatment with antibiotics and/or systemic corticosteroids. A severe COPD exacerbation is defined as requires hospitalization.

The details of the planned displays are in Appendix 12: List of Data Displays.

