6.2.8. Adverse Events

The investigator or site staff will be responsible for detecting, documenting and reporting events that meet the definition of an AE or SAE.

AEs will be collected from the start of double-blind Investigational Product and until the follow up contact.

COPD exacerbations should not be recorded as an adverse event, unless they meet the definition of a Serious Adverse Event. For the purposes of this study, COPD exacerbations will be collected and recorded on the COPD exacerbation log in the eCRF. The time period for collection of COPD exacerbations will begin from the time of Visit 2 (Randomization) and will end when the 7-day Follow-up period has been completed.

The investigators and site staff should remain vigilant for the possible development of pneumonia in patients with COPD as the clinical features of such infections overlap with the symptoms of COPD exacerbations. Risk factors for pneumonia in patients with COPD receiving fluticasone furoate/vilanterol include current smokers, patients with a history of prior pneumonia, patients with a body mass index $<25 \text{ kg/m}^2$ and patients with an FEV₁<50% predicted. For all suspected cases of pneumonia, Investigators are encouraged to confirm the diagnosis (this includes obtaining a chest x-ray) and to initiate appropriate therapy as promptly as possible. All diagnoses of pneumonia (radiographically confirmed or unconfirmed) must be reported as an AE or SAE (if applicable).

All AEs and SAEs will be followed until resolution, until the condition stabilizes, until the event is otherwise explained, or until the subject is lost to follow-up. Once resolved,

the appropriate AE/SAE CRF page will be updated. The investigator will ensure that follow-up includes any supplemental investigations as may be indicated to elucidate the nature and/or causality of the AE or SAE. This may include additional laboratory tests or investigations, histopathological examinations, or consultation with other health care professionals.

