8.3.5.2.5. COPD Exacerbations and Pneumonias

The number of moderate or severe COPD exacerbations and the percent of patients experiencing moderate or severe COPD exacerbations will be summarized.

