# 9.4.3. Study Phases for Adverse Events and All Other Data Recorded in Logs (excluding Concomitant Medications)

Study Phase	Definition
Pre-Treatment	Event Onset Date < Study Treatment Start Date
On-Treatment	Study Treatment Start Date ≤ Event Onset Date ≤ Study Treatment Stop Date + 1
Post-Treatment	Event Onset Date > Study Treatment Stop Date + 1

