#### **Extent of Exposure**

- Number of days of exposure to study drug will be calculated based on the formula:
  - Duration of Exposure in Years = (Treatment Stop Date (Treatment Start Date) + 1) / 365.25
- This will also be the exposure used to calculate rate of events
- Duration of exposure will be summarised by the following categories:
  - $\leq$  3months.
  - > 3 months < to  $\le$  6 months.
  - > 6 months to  $\leq$  12 months,
  - >12 months to  $\leq$  24 months.
  - >24 months to ≤ 36 months and
  - >36 months

where 1 month is equal to (365.25 days/12).

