#### Rate of Adverse Events per 100 Treatment Years

Rate of on-treatment adverse events per 100 treatment years will be calculated using:

Rate = number of events \* 100 / total treatment exposure in years

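### SAP 7.7 summarises exacerbations by subject only: the event count planned in the protocol is missing without notice, and there is no exposure-adjusted rate as there is for fractures and pneumonia

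*SAP*

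**What the plan says.** Protocol 8.3.5.2.5 plans two quantities: "The number of moderate or severe COPD exacerbations and the percent of patients experiencing moderate or severe COPD exacerbations will be summarized".

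SAP 7.7 plans "The number and percentage of subjects reporting an on-treatment moderate/severe exacerbation along with the outcome category", followed by result (such as steroid or antibiotic treatment, or hospitalisation) and primary cause. It mentions neither a number of events nor a rate. SAP Table 1, which sets out departures from the protocol analysis, covers the BMD model, the population and the power table, and says nothing on exacerbations.

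The two preceding sections go further. SAP 7.5 says "In addition, the rates of fractures will be summarised as described in Section 9.6.3", and SAP 7.6 says "In addition, the rates of events will be summarised as described in Section 9.6.3". Both also show how many events subjects had.

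The means of computing a rate are already in the SAP. Section 9.6.3 gives "Rate = number of events \* 100 / total treatment exposure in years", and Section 9.6.2 says of treatment exposure: "This will also be the exposure used to calculate rate of events". Under Section 9.4.3, an event recorded in a log is on-treatment if "Study Treatment Start Date ≤ Event Onset Date ≤ Study Treatment Stop Date + 1".

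**The concern.** A subject can have several exacerbations in 156 weeks. A count of subjects treats six events like one, and treats someone who leaves event-free after four months like someone event-free for three years. Because counting ends with treatment, each subject's chance of appearing in the numerator depends on time on treatment. If the arms differ in that time, the percentages can differ with no difference in underlying rate, or can conceal a real one.

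The adverse event tables do not fill the gap. Protocol 6.2.8 says: "COPD exacerbations should not be recorded as an adverse event, unless they meet the definition of a Serious Adverse Event". Moderate exacerbations that are not serious therefore stay out of the adverse event rates.

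At stake is the reading of a named endpoint in the group of other endpoints, and a summary that the protocol planned and the SAP text no longer contains.

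**Working it through.** **Comparing the texts**

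| | Subjects, n and % | Number of events | Rate per 100 treatment years |
|---|---|---|---|
| Protocol 8.3.5.2.5, exacerbations | % planned | planned | not planned |
| SAP 7.7, exacerbations | planned | not stated | not stated |
| SAP 7.5, fractures | planned | incidents per subject | planned |
| SAP 7.6, pneumonia | not spelled out | events per subject | planned |

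Two separate points follow. The event count was in the protocol and is absent from the SAP text. The rate was never in the protocol; its absence is an inconsistency within the SAP.

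**Illustrating the size**

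The plan states no figure for exacerbations, so there is none to reproduce.

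*From the documents.* Treatment lasts 156 weeks, so T = 1092/365.25 = 2.99 years. The protocol aims for 224 completers among 280 randomised, 224/280 = 80%, or 140 randomised per arm.

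*Assumed, because not given.* The true exacerbation rate λ is 0.2, 0.4 or 0.8 per year and the same in both arms. Completion c is 80% v 80%, 85% v 75% or 90% v 70%, each averaging the planned 80%. Discontinuation has a constant hazard, and events follow a Poisson process. The one-day extension after stopping is ignored.

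*Formulae.*
- Discontinuation hazard: h = −ln(c)/T
- Mean time on treatment: (1 − c)/h
- Probability of at least one on-treatment event: λ/(λ + h) × [1 − exp(−(λ + h)T)]

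*Worked case, λ = 0.4.*
- c = 0.9: h = 0.0352, mean exposure 2.84 years, probability 0.4/0.4352 × (1 − exp(−1.301)) = 0.669
- c = 0.7: h = 0.1193, mean exposure 2.51 years, probability 0.4/0.5193 × (1 − exp(−1.553)) = 0.607
- Gap: 6.2 points

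*All cases: percentage with an event, arm A v arm B. The gap in brackets is taken from unrounded values.*

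| Completion | Mean years on treatment | λ = 0.2 | λ = 0.4 | λ = 0.8 |
|---|---|---|---|---|
| 80% v 80% | 2.68 v 2.68 | 40.8 v 40.8 (0) | 63.9 v 63.9 (0) | 84.8 v 84.8 (0) |
| 85% v 75% | 2.76 v 2.60 | 41.9 v 39.7 (2.2) | 65.4 v 62.3 (3.1) | 86.4 v 83.1 (3.2) |
| 90% v 70% | 2.84 v 2.51 | 42.9 v 38.5 (4.4) | 66.9 v 60.7 (6.2) | 87.9 v 81.5 (6.4) |

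If rates vary between subjects (gamma-Poisson, dispersion 1), the gaps shrink to 1.7 to 2.4 points at 85% v 75% and 3.5 to 4.8 points at 90% v 70%. The expected Section 9.6.3 rate is the same in both arms in every case: 20, 40 or 80 per 100 treatment years.

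*Masking.* Let arm B's true rate be 25% higher (0.25 v 0.2, or 0.5 v 0.4). At 80% v 80% completion the percentages differ by 7.0 to 7.5 points. At 90% v 70%, with arm B the shorter-exposed, they differ by only 1.2 to 2.3 points (Poisson).

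*Count alone.* With 140 subjects per arm, λ = 0.4 and 90% v 70% completion, expected events are 140 × 0.4 × 2.84 = 159 and 140 × 0.4 × 2.51 = 141 at the same true rate. Restoring the count meets the protocol but does not remove the dependence on exposure.

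**The case against.** The strongest reply is that little is lost.

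- **The endpoint is descriptive.** Exacerbations are one of the other endpoints, with no test planned. This stands and limits the weight of the point.
- **Part of the information appears elsewhere.** Severe exacerbations have Table 2.25. Because they require hospitalisation, they should generally also enter the serious adverse event tables, of which Table 2.42 shows occurrences and rates. Every exacerbation is in Listing 28, and Table 2.1 summarises exposure. This stands for severe events. For moderate events outside hospital, a listing is not a summary by arm.
- **The table shell is not available.** Tables 2.24 and 2.25 use shell SAFE_T09, which is not in the documents and may carry counts or rates. The lack of a note asking for rates proves nothing, since the pneumonia and fracture tables lack one too. This stands: the finding concerns what the SAP text commits to.
- **The asymmetry may have a reason.** The Section 9.6.3 formula is headed for adverse events. Pneumonia is reported as one; exacerbations are not unless serious. That may explain the omission, but the arithmetic applies equally to logged exacerbations.

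A reader might also infer more than the documents support:

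- **That pneumonia and exacerbations cannot be compared.** Pneumonia is an event of special interest in Table 2.47, and protocol 8.3.5.2.2 calls for the number and percentage of subjects for adverse events. A pneumonia percentage should therefore be available, and SAP 7.6 also reports pneumonias close to an exacerbation.
- **That the count measures systemic-steroid courses.** A moderate exacerbation may be treated with antibiotics alone. SAP 7.7 already shows steroid treatment, and Table 1.22 covers medications given for exacerbations.
- **That the planned Kaplan-Meier plot shows unequal discontinuation was expected.** The SAP gives no reason for the plot.

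**Conclusion.** The point holds as a minor one. SAP 7.7 leaves out the protocol's event count without declaring it, and offers no exposure-adjusted rate although the two sections before it do.

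It does not follow that the exacerbation comparison is confounded. Distortion needs unequal time on treatment, and the documents give no discontinuation by arm. Nor did the SAP drop a planned rate, because the protocol never planned one. The supportable statement is that the crude percentage is open to distortion if exposure differs.

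Under the assumed rates, completion figures, constant hazards and Poisson events, that distortion is 0 points at equal completion, 2.2 to 3.2 points at 85% v 75% and 4.4 to 6.4 points at 90% v 70%. Overdispersion lowers the last two to 1.7 to 2.4 and 3.5 to 4.8 points. The primary BMD analysis is unaffected.

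**What to change.** In SAP 7.7 and Tables 2.24 and 2.25, add by arm the number of on-treatment events (moderate/severe, and severe alone) and the rate per 100 treatment years, using the Section 9.6.2 exposure and the Section 9.6.3 formula. Keep the number and percentage of subjects beside them. State in 9.6.3 that the formula also applies to exacerbations, and list the added rate in Table 1. If shell SAFE_T09 already holds these rows, only the text needs changing.

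The cost is a sentence in 7.7, a few words in 9.6.3, an entry in Table 1 and a few rows in two tables. No new data are needed, since each exacerbation is already recorded in the eCRF log.

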# 7.8. Clinical Laboratory Analyses

Laboratory evaluations including the analyses of Chemistry laboratory tests, Hematology laboratory tests, and liver function tests will be based on GSK Core Data Standards. The details of the planned displays are in Appendix 12: List of Data Displays.

# 7.9. Vital Signs and Non-Laboratory Analyses

The analyses of non-laboratory safety test results including vital signs will be based on GSK Core Data Standards, unless otherwise specified.

# 9. APPENDICES

# 9.1. Appendix 1: Protocol Deviation Management and Definitions for Per Protocol Population

# 9.1.1. Exclusions from Per Protocol Population

There will be no per protocol population analysed in this study.

# 9.2. Appendix 2: Schedule of Activities

Protocol Defined Schedule of Events

			Double-Blind Treatment period														
Visit Number	0 Pre- screen 	1 Screen- ing 	2 Random- ization	3	4	5	6	7	8	9	10	11	12	13	14	Early With- draw	15 Follow -up
			Day 1	13 wks ±14 Days	26 wks ±14 Days	39 wks ±14 Days	52 wks ±14 Days	65 wks ±14 Days	78 wks ±14 Days	91 wks ±14 Days	104 wks ±14 Days	117 wks ±14 Days	130 wks ±14 Days	143 wks ±14 Days	156 wks ±14 Days	- GIGIT	Visit 14/EW + 7±2 Days
Assessments																	
Informed consent 	X																
PGx Consent & Sampling 			x														
Demography	X																
Medical History		X															
Physical Exam		X					Х				Х				X	X	
Spirometry Testing		X	X		X		X		X		X		X		X	X	
Reversibility Testing		Х															
Smoking history/ smoking status		X	X	Х	Х	Х	Х	Х	Х	Х	Х	Х	Х	X	X	Х	
Smoking cessation counseling		X					х				х				х	X	
Register visit on IVRS 	X	х	х	Х	х	х	Х	Х	х	х	х	Х	х	х	х	х	X
Safety Assessments																	
BMD DEXA scans 		X			Х		X		X		X		X		X	X	
Oropharyngeal examination 		X	X	х	х	х	х	X	Х	х	х	х	х	X	x	х	
Chest X-ray 		Х															
Lab Tests  / Serum Pregnancy Test 		х															

							Dou	ble-Blind	Treatme	ent perio	d						
Visit Number	0 Pre- screen1	1 Screen- ing 	2 Random- ization	3	4	5	6	7	8	9	10	11	12	13	14	Early With- draw	15 Follow -up
			Day 1	13 wks ±14 Days	26 wks ±14 Days	39 wks ±14 Days	52 wks ±14 Days	65 wks ±14 Days	78 wks ±14 Days	91 wks ±14 Days	104 wks ±14 Days	117 wks ±14 Days	130 wks ±14 Days	143 wks ±14 Days	156 wks ±14 Days		Visit 14/EW + 7±2 Days
12-lead ECG & Rhythm Strip		х															
Exacerbation Assessment		Х	Х	X	X	X	X	X	X	X	X	X	X	Х	X	X	Х
Adverse Event Assessment 			Х	X	X	X	X	X	X	X	X	X	X	X	X	X	X
Serious Adverse Event Assessment 	Х	Х	Х	X	X	X	X	X	X	X	X	X	X	X	X	X	X
Dispense Diary		Х	X	X	X	Х	X	X	X	X	X	X	Х	X			
Collect/Review Diary			X	X	X	X	X	X	X	X	X	X	X	X	X	X	
Medication Assessments																	
Concurrent Medication Assessment 	х	x	х	k	х	Х	Х	х	Х	х	Х	х	Х	Х	х	х	x
Dispense albuterol (salbutamol) 		Х	х	Х	Х	Х	Х	Х	Х	Х	Х	Х	Х	Х			
Collect albuterol (salbutamol) 			х	Х	Х	Х	Х	Х	Х	Х	Х	Х	Х	Х	X	Х	
Dispense Single-Blind Medication		х															
Dispense Double- Blind Medication			х	Х	х	Х	Х	Х	Х	Х	х	Х	Х	Х			
Collect Blinded Medication			Х	Х	Х	Х	Х	Х	Х	Х	Х	Х	Х	Х	Х	Х	
Other Assessment																	

				Double-Blind Treatment period													
Visit Number	0 Pre- screen 	1 Screen- ing 	Random- ization	3	4	5	6	7	8	9	10	11	12	13	14	Early With- draw	15 Follow -up
			Day 1	13 wks ±14 Days	26 wks ±14 Days	39 wks ±14 Days	52 wks ±14 Days	65 wks ±14 Days	78 wks ±14 Days	91 wks ±14 Days	104 wks ±14 Days	117 wks ±14 Days	130 wks ±14 Days	143 wks ±14 Days	156 wks ±14 Days		Visit 14/EW + 7±2 Days
Discharge from Study 															Х	Х	

- Visit 0 and Visit 1 may occur on the same day if the subject does not take or has not taken any protocol excluded medications.
- Following Screening Visit 1, subjects enter a 14 to 21 day single-blind run-in period.
- Subjects will be assigned a subject number at the time ICF is signed. The ICF must be signed before any study procedures including medication exclusion period(s).
- Saliva (2ml) sample is collected in the DNA self-collection kit. This should ideally be taken as soon after randomization (Visit 2) as possible, but may be taken at any other visit
  after randomization if necessary. PGx consent must be signed prior to PGx sampling.
- A telephone based IVRS system (RAMOS) which will be used by the investigator or designate to register the subject, randomize the subject and provide medication assignment information.
- Baseline BMD measurements will be collected between Visit 1 and Visit 2.
- If evidence of infection, culture swab may be taken and appropriate therapy should be instituted at Investigator discretion. Subjects with culture-positive infection may continue in the study on appropriate anti-infective treatment at Investigator discretion.
- 8. Chest X-ray must be taken if a Chest X-ray or CT scan is not available within the 12 months preceding Visit 1. Chest x-rays will be requested for suspected cases of pneumonia.
- Non-fasting and pre-dose. A blood sample for repeat analysis is collected only if any part of Screening lab needs to be repeated. Results of repeat labs should be received prior to Randomization at Visit 2.
- 10. Females of child-bearing potential only
- Adverse events are to be collected from the start of blinded study medication (Visit 2) until the follow-up phone contact.
- Serious adverse events are to be collected from the start of study drug (Visit 2) until the follow-up phone contact. However, any SAEs assessed as related to study participation
  will be recorded from the time subjects sign informed consent.
- 13. All COPD medications taken within 30 days prior to Visit 0 will be collected.
- Collect and re-dispense as needed after Visit 1.
- Discharge from study on appropriate therapy.

# 9.3. Appendix 3: Assessment Windows

# 9.3.1. Definitions of Assessment Windows for Analyses: BMD Data

Analysis Set	Target	Analysis	Window	Analysis		
/ Domain		Beginning Timepoint	Ending Timepoint	Timepoint		
ITT", "Safety"	Week 26	Day 2	Day 272	VISIT 4		
ITT", "Safety"	Week 52	Day 273	Day 454	VISIT 6		
ITT", "Safety"	Week 78	Day 455	Day 636	VISIT 8		
ITT", "Safety"	Week 104	Day 637	Day 818	VISIT 10		
ITT", "Safety"	Week 130	Day 819	Day 1000	VISIT 12		
ITT", "Safety"	Week 156	Day 1001	Day 1182	VISIT 14		

In order to include all bone mineral density assessments, the analysis window has been increased to  $\pm$  3 months. A schematic of the above windowing is given below.

	273 454		637 818	-	1001 1182
Week 26 Visit 4	Week 52 Visit 6	Week 78 Visit 8	Week 104 Visit 10	Week 130 Visit 12	Week 156 Visit 14
2 272		455 636	-	819 1000	-

If there are multiple assessments within a window these will be averaged on the raw scale (i.e. before log transformation).

